### 8.1.2 List of Graphs

- Boxplots of background-adjusted IFN- $\gamma$  and/or IL-2 response magnitude by T-cell subset, HIV protein, visit, and treatment arm. [*Treatment groups side by side per protein, one T-cell subset and one visit per graph.*]
- For PT reports #2 and #3 when data from multiple visits are available, Spaghetti plots background-adjusted IFN- $\gamma$  and/or IL-2 response magnitude by T-cell subset, HIV protein, visit, and treatment arm. [*Treatment groups side by side per protein, one T-cell subset and one visit per graph.*]

## 8.2 Neutralizing Antibody

Neutralization assays will measure titers in TZM-bl cells against BG505/T332N and MW965.26 with samples from: Baseline (visit 1), 2 weeks post 3rd dose (visit 7), 2 weeks post 4th dose (visit 9), and 6 months post 4th dose (visit 10). Positivity calls will be an unrounded ID50 value  $\geq 10$ , the starting dilution, which is the limit of detection of the assay. Any samples resulting in  $>100$  ID50 titer against BG505/T332N will be tested against a 12-virus panel used to assess heterologous tier 2 neutralization grown in 293T/17 cells.

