Figure 2-1 In vitro and in vivo characterization of sD-NLT-AB05. (A) Size-exclusion chromatography elution showing homogenous trimers are produced (B) Negative stain electron microscopy imaging of NLT-AB05 (C) Antigenic profile of NLT-AB05 (D) Muscle sections from mice treated intramuscularly with DNA-encoded BG505(gp120)foldon or sD-NLT-AB05 Stained with known monoclonal Abs recognizing either well folded trimers (PGT145) or poorly folded trimers (3074). Staining with non-nAb 3074 indicates poorly folded trimer while staining with bnAb PGT145 indicates well-folded trimer.

[figure not shown]

Figure 2-2 Immunogenicity of sD-NLT-AB05. (A) Comparison of BG505 Env-specific cellular responses in naïve mice or mice immunized with pVAX plasmid backbone, Sigma Adjuvant System (RIBI)-co-formulated protein BG505.MD39, or sD-NLT-AB05 without adjuvant by IFN γ ELISPOT assay (left panel) or intracellular cytokine staining (right panel). Cells were stimulated with overlapping 15-mer peptide pools for wild-type BG505 gp140 divided into 3 pools from N-terminus to C-terminus. (B) Left panel: Binding antibodies induced by sD-NLT-AB05 comparable to RIBI-co-formulated protein BG505.MD39 immunizations. Right panel: Unique induction of autologous tier-2 neutralizing responses by sD-NLT-AB05 in contrast to recombinant protein. DNA (short) = immunization at weeks 0, 3, 6. DNA (long) = immunization at weeks 0, 3, 16.

[figure not shown]

Figure 2-3 Immunogenicity of sD-NLT-AB05. (A) Neutralization ID50 titers of heat-inactivated mice sera for sD-NLT-AB05 immunized mice with strong neutralizing activity against listed pseudovirus isolates. Isolated nAbs using antigen-specific B-cell sorting of sD-NLT-AB05 immunized mice. IC50 values of trimer-specific murine mAbs for BG505.T332N, BG505.T332N.T465N or MLV. (B) Structural model of nAb clone C24 with positions mutated from the germline sequences are displayed in red. Cryo-EM structure of C24 in complex with BG505.MD39.

2.3 Clinical Experience with related DNA vaccines encoding HIV Env immunogens with and without IL-12 adjuvant

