5.1.1 Inclusion criteria

1. Able and willing to complete the informed consent process, including an Assessment of Understanding: volunteer demonstrates understanding of this study; completes a questionnaire prior to first vaccination with verbal demonstration of understanding of questionnaire items that were answered incorrectly.
2. 18-55 years old, inclusive, on day of enrollment.
3. Available for clinic follow-up through the last clinic visit and willing to be contacted 12 months after the last vaccine administration.
4. Agrees not to enroll in another study of an investigational agent during participation in the trial.
5. In good general health according to the clinical judgment of the site investigator.
6. Physical examination and laboratory results without clinically significant findings that would interfere with assessment of safety or reactogenicity in the clinical judgement of the site investigator.
7. Assessed as low risk for HIV acquisition per low risk guidelines (see [Appendix D](#)), agrees to discuss HIV infection risks, agrees to risk reduction counseling, and

agrees to avoid behavior associated with high risk of HIV exposure through the final study visit. Low risk may include persons stably taking PrEP as prescribed for 6 months or longer.

8. Hemoglobin:

- ≥ 11.0 g/dL for volunteers who were assigned female sex at birth
- ≥ 13.0 g/dL for volunteers who were assigned male sex at birth and transgender men who have been on hormone therapy for more than 6 consecutive months
- ≥ 12.0 g/dL for transgender women who have been on hormone therapy for more than 6 consecutive months
- For transgender participants who have been on hormone therapy for less than 6 consecutive months, determine hemoglobin eligibility based on their sex assigned at birth

9. White blood cell (WBC) count = 2,500-12,000/mm³ (not exclusionary: if count greater than 12,000 with investigation showing general good health and PSRT approval).

10. Platelets = 125,000-550,000/mm³

11. Alanine aminotransferase (ALT) $< 2.5 \times$ upper limit of normal (ULN) based on the institutional normal range

12. Serum creatinine $\leq 1.1 \times$ ULN based on the institutional normal range

13. Blood pressure in the range of 90 to < 140 mmHg systolic and 50 to < 90 mmHg diastolic.

14. Negative results for HIV infection by a Food and Drug Administration (FDA)-approved enzyme immunoassay (EIA) or chemiluminescent microparticle immunoassay (CMIA).

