2. NON-SEXUAL BEHAVIORS

In the **last 12 months**, did not:

- Inject drugs or other substances without a prescription
- Use cocaine, methamphetamine, or excessive alcohol, which in the investigator's judgment, rendered the participant at greater than low risk for acquiring HIV infection.
The investigator's judgment should consider local epidemiologic information about HIV prevalence in the area and community networks.

A volunteer is NOT appropriate for inclusion if he/she/they:

Acquired an STI (ie, new infection) in the **last 12 months**:

- Syphilis
- Gonorrhea
- Non-gonococcal urethritis
- Herpes Simplex Virus type 2 (HSV2)
- Chlamydia
- Pelvic inflammatory disease (PID)
- Trichomonas
- Mucopurulent cervicitis
- Epididymitis
- Proctitis
- Lymphogranuloma venereum

- Chancroid
- Hepatitis B

For US volunteers on PrEP

1. PrEP ASSESSMENT

- Reports six months (180 days) or more of protective PrEP use
- For daily oral PrEP use:
 - For persons AMAB who have sex with persons AMAB: Reports equal to or greater than 70% when asked the following: *“Thinking about the past 4 weeks, what percent of the time were you able to take all your PrEP medications?”*
 - For people with a vagina having intravaginal intercourse: Reports equal to or greater than 90% when asked the following: *“Thinking about the past 4 weeks, what percent of the time were you able to take all your PrEP medications?”*
- For event-driven (on-demand or “2-1-1”) PrEP use¹ in persons AMAB who have sex with persons AMAB: Reports use consistent with the guidance of the professional education organization, the International Antiviral Society–USA (IAS-USA):
 - For individuals with frequent use (> 15 pills per month): At least 80% of condomless sex acts are covered with on-demand PrEP at the recommended dose schedule
 - For individuals with less frequent use (\leq 15 pills per month):
 - A past history of high adherence (> 90%)
 - Commitment to use on-demand PrEP for *all* condomless sex acts at the recommended dose schedule
- For long-acting agents, such as injectable cabotegravir, please consult with the PSRT.
- Commits to maintaining protective PrEP use throughout trial

¹ See Study-specific Procedures (SSP) for additional guidance on on-demand PrEP.

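### SAP 8.2 calls neutralization on ID50 of at least 10 alone, although participants on continuing PrEP may enrol; the protocol and SAP state no way to separate antiretroviral inhibition from vaccine-induced antibody

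*SAP*

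**What the plan says.** **Eligibility.** Inclusion criterion 7 (Protocol 5.1.1) states: "Low risk may include persons stably taking PrEP as prescribed for 6 months or longer". Appendix D accepts daily oral and event-driven use. For injectables it says: "For long-acting agents, such as injectable cabotegravir, please consult with the PSRT". A PrEP user is eligible only if he or she "Commits to maintaining protective PrEP use throughout trial".

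**Assay and visits.** SAP 8.2: "Neutralization assays will measure titers in TZM-bl cells against BG505/T332N and MW965.26 with samples from: Baseline (visit 1"), and at Visits 7, 9 and 10.

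**Positivity.** SAP 8.2: "Positivity calls will be an unrounded ID50 value" of at least 10, described as "the starting dilution, which is the limit of detection of the assay". No other condition is given.

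**Follow-on testing.** A sample with a titre above 100 against BG505/T332N "will be tested against a 12-virus panel used to assess heterologous tier 2 neutralization grown in 293T/17 cells".

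**Related rules.** SAP 7.2 excludes unreliable assay results without defining the term. It tests magnitude with Wilcoxon tests on all available data, whether or not the sample is positive, and replaces values below the detection limit by half that limit. Appendix A of the protocol records concomitant medications, including prescription drugs, at every clinic visit.

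**The concern.** The assay reads a fall in HIV infection of cells. Antibody produces that fall, and an antiretroviral carried over in the serum could produce it too. The cutoff sits at the starting dilution, where any drug is least diluted. Eligible PrEP users are expected to be taking drug at the visits where neutralization is measured, and nothing in SAP 8.2 would separate the two causes.

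What is at stake is secondary endpoint 1a (autologous and tier 1a isolates after the third and fourth vaccinations) and secondary endpoint 3c (autologous tier 2 at 6 months). An inflated titre would also enter the Wilcoxon tests. It could trigger the 12-virus panel, where inhibition of several viruses by a drug might be read as heterologous breadth (exploratory objective 6). There is no placebo group to show the background rate.

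**Working it through.** **1. Rules compared across assays in the SAP**

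| Assay | Baseline in the positivity rule? |
|---|---|
| BAMA (8.6) | Yes: more than 3 times baseline |
| ICABA (8.5) | Yes: mock- and baseline-subtracted |
| ADCC luciferase (8.4) | Yes: baseline subtracted |
| Neutralization (8.2) | No: ID50 of at least 10 only |

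Visit 1 serum is assayed for neutralization but does not enter the call. Followed as written, the rule scores a sample at or above 10 as positive even if the same participant was positive before any vaccine.

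**2. Effect of one drug-driven positive on a response rate**

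Inputs: 10 per group (SAP section 4); 9 evaluable per group after 10% missing data (Protocol 6.1.1). One sample moves the rate by 1/10 = 10 points, or 1/9 = 11.1 points.

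**3. Effect on the planned test**

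SAP 7.2 names Barnard's test, two-sided, significant at p ≤ 0.05. The counts below are illustrations; the documents give no expected neutralization rates.

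| n per arm | Without drug effect | p | With one drug-driven positive | p |
|---|---|---|---|---|
| 10 | 4 v 0 | 0.042 | 4 v 1 (lower arm) | 0.151 |
| 10 | 6 v 0 | 0.004 | 6 v 1 (lower arm) | 0.023 |
| 9 | 5 v 0 | 0.010 | 5 v 1 (lower arm) | 0.057 |
| 9 | 5 v 1 | 0.057 | 6 v 1 (higher arm) | 0.021 |

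A borderline result can be lost or created. A large difference survives one such sample, and 7/10 v 2/10, which allows for two in the lower arm, still gives p = 0.041.

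**4. Effect on magnitude**

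A true negative enters the Wilcoxon test as 10/2 = 5. If drug lifts it to the cutoff, it enters as at least 10 and ranks above every true negative. The size of any lift beyond that is unknown.

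**5. How likely a PrEP user is among the 20**

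PrEP prevalence is not in the documents, so it is assumed. P(at least one) = 1 − (1 − q)^20.

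| Assumed q | P(at least one of 20) |
|---|---|
| 5% | 64% |
| 10% | 88% |
| 20% | 99% |

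This is the chance that a PrEP user is enrolled. It is not the chance of a false positive, which also needs the drug effect at the tested dilution.

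**The case against.** **A check may exist elsewhere.** Protocol 4.1 places technical assay details in the Central Assay Plan and points to separate assay descriptions. Neither was available. A reader might infer that the trial has no drug check; the documents support only that the protocol and SAP state none. This stands. Even so, a laboratory control would still need a SAP rule for how a failed control is analysed.

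**The mechanism is inferred.** No passage says that serum antiretroviral lowers the TZM-bl signal, or by how much. This stands. A reader might also take the Protocol 2.2 figure legend ("IC50 values of trimer-specific murine mAbs for BG505.T332N, BG505.T332N.T465N or MLV") as proof that the team used MLV as a drug control and then dropped it. The legend concerns mouse monoclonal antibodies and does not show that.

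**Visit 1 would often reveal the problem.** PrEP users must report at least 180 days of protective use, so a daily user would normally be on drug at Visit 1, and titres are plotted over time. This narrows the gap but does not close it. The call ignores Visit 1, which is a screening visit up to 56 days before the first vaccination. It would also miss event-driven use, injection timing, or PrEP begun or changed later.

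**Unreliable results can already be excluded, and broad inhibition across 12 viruses would look suspicious.** Both are true. But without a definition, the decision falls after results are seen, in an open-label trial where laboratory blinding holds only when feasible.

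**The example sits on a knife-edge.** Correct for 4/10 v 0/10; the table above shows the larger differences that survive.

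**Conclusion.** The gap holds in limited form. Protocol and SAP together admit continuing PrEP users and apply a positivity rule that would score any drug-inhibited sample as a vaccine response. It touches secondary endpoints 1a and 3c and the exploratory breadth work, not the primary BAMA and T-cell endpoints.

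The size is 10 points of response rate per affected sample (11 at n = 9), enough to change a borderline comparison but not necessarily a large one. This rests on two unknowns: that drug in serum lowers the readout at the dilutions used, and that at least one participant is on PrEP at a neutralization visit.

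A reader might infer that the neutralization results are contaminated, or that PrEP biases the comparison towards one arm. The documents support neither. They give no count of users and no effect size, and PrEP use differs between randomized arms only by chance, though with 10 per arm chance imbalance is easy.

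**What to change.** Amend SAP 8.2; eligibility need not change.

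1. Flag each neutralization sample drawn while the participant was on PrEP, using the concomitant-medication record, before results are seen. If titres have already been reported, the flag should be set by someone without access to them.
2. When a participant's Visit 1 sample is positive for a virus, do not count a later sample as a vaccine response to that virus unless it shows a prespecified rise over Visit 1. The BAMA threefold rule is a precedent within the same SAP; the team should set the factor.
3. Add a sensitivity analysis of response rate, magnitude and the above-100 trigger without PrEP-flagged samples.
4. If the laboratory already runs, or can add, a control virus that differs only in Env and stays sensitive to the drug (for example MLV Env on an HIV backbone), treat a flagged result as unreliable under SAP 7.2 when the control is inhibited at ID50 of 10 or more. A control unrelated to HIV would not do, because an HIV-specific drug need not inhibit it.

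Steps 1 to 3 need no new assay, only SAP text and data already collected. Step 4 is optional and costs one virus on the flagged samples. The downside is that a few neutralization results may be set to missing, and the sensitivity analysis will be smaller still than 10 per arm.

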## 8.4 Antibody-Dependent Cell-mediated Cytotoxicity (ADCC)

The established Luciferase and GranToxiLux (GTL) assays will be used to assess response rates and magnitude of serum ADCC. ADCC assays will be performed on participants' sera for visit 1, visit 7 (M3.5), and visit 9 (M6.5). If sufficient responses are seen against BG505, additional luciferase assays may be done to explore breadth of responses.

For the Luciferase assay, CEM.CCR5.NKR cells infected with HIV-1 IMC BG505 will be tested in a 96-well plate. Participant sera in addition to controls will be incubated with the IMC-infected cells, and ADCC will be detected through the use of Vivirene luminescence. To assess breadth,

CEM.CCR5.NKR cells infected with HIV-1 CAP8, CH058, SUMA, and WITO, and possibly three additional IMCs, individually, will be tested.

For the GTL assay, CEM.CCR5.NKR cells coated with Clade A BG505 gp120 will be tested in a 96-well plate. Participant sera in addition to controls will be incubated with the HIV protein, and ADCC will be detected through the use of granzyme B substrate.

The following assay readouts will be used in the analyses for these assays:

- i) Luciferase: The data from the luciferase assay is semiquantitative. The peak of specific killing and area under the curve (AUC) will be summarized by treatment group.
- ii) GTL: The data from the assay is quantitative. The frequency of positive responses (% responders) peak ADCC, and area under the curve (AUC) will be summarized by treatment group.

Positivity criteria are as follows:

- i) Luciferase: peak % loss Luciferase activity  $\geq 10\%$ , after background subtraction of baseline response and if responses are positive at one of the first two dilutions. For example, if the first two dilutions (1:50 and 1:200) are negative, regardless of 1:800 % loss Luciferase activity, 1:800 is negative.
- ii) GTL: peak activity  $\geq 8\%$

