#### 8.5 Infected cells antibody binding assay (ICABA)

The ICABA assay is conducted to address the exploratory objective to evaluate Ab avidity and Fc Receptor functions. ICABA will detect the presence of antibodies binding to the surface of HIV-1 infected cells in the serum of participants using Infectious Molecular Clone (IMC)-infected target cells.

The ICABA assays will be performed on participants' sera for visit 1, visit 7 (M3.5), and visit 9 (M6.5). CEM.CCR5.NKR cells infected with HIV-1 IMC BG505 and mock-infected cells will be tested in a 96-well plate. Participant sera in addition to controls will be incubated with the IMC-infected cells and the presence of bound antibodies will be detected on the surface of the cells using flow cytometry. The % of IgG+ cells is considered positive if the infected cell mock- and baseline-subtracted %IgG+ at 1:100 dilution is >5%.

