## 8.6 Binding Antibody Multiplex Assay (BAMA)

The Binding Antibody Multiplex Assay (BAMA) assay will evaluate binding antibody responses of each serum specimen against BG505 SOSIP (vaccine trimer immunogen) and Trimer 4571 (vaccine matched immunogen). The time points to be tested are: Visit 1 (baseline), Visit 5 (Month 1.5, 2 weeks post 2nd vaccination), Visit 7 (Month 3.5, 2 weeks post 3rd vaccination), 9 (Month 6.5, 2 weeks post 4th vaccination), and Visit 10 (Month 12, 6 months post 4th vaccination). Specimens from other time points as well as other HIV antigens and antibody isotypes may be assayed based on the results of the initial assay.

The following readouts, if included in the final Central Assay Plan, will be analyzed for this assay:

- i. Binding Mean Fluorescence Intensity (MFI): The frequency of positive responders (%) will be tabulated to assess HIV binding antibody responses between vaccine groups from MFI readouts. Positivity criteria include (1) the net MFI (MFI – Blank) values are  $\geq$  antigen-specific cutoff at the 1:50 dilution level for IgG (based on the 95th percentile of the baseline visit serum samples and at least 100 MFI minus Blank), (2) the net MFI values are greater than 3 times the baseline (day 0) net MFI, and (3) the MFI values are greater than 3 times the baseline MFI values.
- ii. Titration (EC50/AUC): If high binding magnitude is observed and it is deemed scientifically important by the lab PI, samples may be titrated to calculate antibody titers. The geometric mean titer will be compared between vaccine groups. The overall difference in geometric mean titer between groups at each time point assays will be compared.
- iii. Differential Binding Response: Epitope specificities may be assessed via wildtype-mutant pairs.

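### Neutralization and GTL ADCC positivity rules leave out the Visit 1 result, so unchanged baseline activity counts as a vaccine response (minor: secondary and exploratory responder tables only)

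*SAP*

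**What the plan says.** SAP 8.2 measures neutralization at Visit 1 (baseline) and Visits 7, 9 and 10. Its rule reads "Positivity calls will be an unrounded ID50 value" of at least 10, and it describes 10 as "the starting dilution, which is the limit of detection of the assay". SAP 8.4 tests ADCC on sera from Visits 1, 7 and 9. The GTL rule is "GTL: peak activity" of at least 8%. Neither rule has a term for the participant's own Visit 1 value.

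Other assays in the same SAP do use that value. ICABA positivity rests on the "infected cell mock- and baseline-subtracted %IgG+ at 1:100 dilution". One of the three BAMA criteria is that "the net MFI values are greater than 3 times the baseline (day 0) net MFI". Luciferase ADCC, in the same section as GTL, subtracts the baseline response before applying its 10% threshold. B-cell phenotyping tests post-vaccination counts against Visit 1 counts.

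The neutralization outputs (SAP 8.2.1) include response rates by visit and arm, summaries among responders and among all participants, and a comparison of arms by visit in rate and/or magnitude. The GTL outputs (SAP 8.4.1 and 8.4.2) include response rates and both kinds of summary, with no listed comparison of arms.

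**The concern.** Both groups of 10 receive active vaccine, so no placebo arm shows how often serum from an unvaccinated person reaches the cut-off. Visit 1 is the control available for that, and the neutralization cut-off sits at the lowest value the assay can detect. A participant who is at or above the cut-off at Visit 1 and does not change is reported as a responder at every later visit tested. At stake are the within-arm response rates, the composition of the responder-only summaries, and the sharpness of any between-arm comparison of neutralization response rates.

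**Working it through.** **1. Rules side by side (SAP section 8)**

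| Assay | Visit 1 assayed | Visit 1 in the positivity rule |
|---|---|---|
| Neutralization (8.2) | yes | no: ID50 at least 10 |
| GTL ADCC (8.4) | yes | no: peak at least 8% |
| Luciferase ADCC (8.4) | yes | yes: baseline-subtracted |
| B-cell phenotyping (8.3) | yes | yes: tested against Visit 1 |
| ICABA (8.5) | yes | yes: mock- and baseline-subtracted |
| BAMA (8.6) | yes | yes: more than 3 times baseline |

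The contrast is sharpest within SAP 8.4, where the same sera and visits are baseline-corrected for luciferase and not for GTL. The SAP gives no reason.

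**2. The plan's own figures.** The documents attach no figure to neutralization or GTL response rates. The nearest is Protocol Table 6-2 (Agresti-Caffo intervals, 9 per arm), which shows what one extra responder does. With p = (x+1)/11 in each arm:
- 5 vs 0 responders: 6/11 − 1/11 = 0.4545; standard error √(0.5455×0.4545/11 + 0.0909×0.9091/11) = 0.1734; interval 11.5 to 79.4 points, as printed.
- 5 vs 1 responders: 6/11 − 2/11 = 0.3636; standard error √(0.5455×0.4545/11 + 0.1818×0.8182/11) = 0.1899; interval −0.9 to 73.6, as printed.

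One false responder in the lower arm is enough to bring zero inside the interval. One in the higher arm would widen the gap instead.

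**3. Chance of at least one baseline-positive.** Let b be the share of participants positive at Visit 1 for a given virus or assay. The documents do not give b, so a range is assumed. Among 20 participants the chance is 1 − (1 − b)^20:
- b = 2%: 1 − 0.98^20 = 33%
- b = 5%: 1 − 0.95^20 = 64%
- b = 10%: 1 − 0.90^20 = 88%

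Within one arm of 10, the chance is 40% at b = 5% and 65% at b = 10%.

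**4. Effect on an arm's rate.** One false responder adds 1/10 = 10 points, or 1/9 = 11.1 points with the Protocol's 10% missing data. This applies only if the participant stays positive and would not have responded anyway. If v is the true vaccine-induced rate and baseline-positives stay positive, the expected observed rate is b + (1 − b)v. The inflation is b(1 − v), which shrinks as v rises.

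**5. Effect on the arm comparison.** With the same b in both arms, the expected difference is (1 − b)(v2 − v1), which is smaller but has the same sign. For illustrative true rates of 0% vs 50%, 9 per arm, and the SAP's two-sided Barnard test at 0.05 (exact enumeration):

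| Assumed b | Expected observed rates | Difference (points) | Power |
|---|---|---|---|
| 0% | 0% vs 50% | 50 | 0.75 |
| 5% | 5% vs 52.5% | 47.5 | 0.60 |
| 10% | 10% vs 55% | 45 | 0.49 |

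**6. Provisions that might already cover this.** By-visit tables and, for neutralization, spaghetti plots can show Visit 1 values. SAP 7.2 allows McNemar and signed-rank tests between visits but names no baseline comparison. None of these changes the positivity call, the response rate computed from it, or who enters the responder-only summaries.

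**The case against.** Much of the case on the other side stands.

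- **Endpoints.** The secondary neutralization endpoints are magnitude and breadth, not response rate, and SAP 7.2 tests magnitude on all available data whatever the positivity call. GTL ADCC is exploratory. A reader might infer that a primary endpoint or the main neutralization comparison is compromised. The documents do not support that: only responder tables are touched.
- **Direction.** A reader might infer that the rule favours one arm. Randomization balances baseline positivity in expectation, so the contrast is diluted. Any imbalance in a given sample of 20 is chance.
- **Visibility.** Visit 1 results are not discarded. By-visit tabulation would reveal baseline-positives, although it would not reclassify them.
- **Likelihood.** Participants must be HIV-negative, and previous recipients of investigational HIV vaccines are excluded (Protocol 5.1). True prior immunity should be rare, so the issue is mainly non-specific activity near the detection limit, at an unknown frequency.
- **Consistency.** Not every assay uses baseline. ICS compares each sample with its own unstimulated control, and EMPEM records detection with no baseline visit listed. Rules are assay-specific, so differing from BAMA is not an error in itself. But ICS has a within-sample control in its rule, and SAP 8.2 and 8.4 state no equivalent in the neutralization or GTL rule.
- **Assay detail.** The SAP does not say how GTL peak activity is background-corrected, and Protocol 4.1 places technical detail in the Central Assay Plan, which was not available. That plan may narrow the GTL part of this point.

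**Conclusion.** The point holds and is minor. As written, the neutralization and GTL rules count unchanged Visit 1 activity as a response. This inflates within-arm response rates, adds unchanged values to the responder-only summaries, and weakens the between-arm rate comparison without pushing it towards either arm. All-participant magnitude tests and the primary endpoints are not affected.

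The size rests on baseline positivity, which is assumed throughout. If it is zero, nothing changes. If it is 2 to 10%, at least one affected participant among 20 has a 33 to 88% chance. A reader might take the 10 to 11 points per participant as a general bias. It applies only to someone who stays positive and would otherwise be a non-responder.

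**What to change.** In SAP 8.2, call a post-vaccination sample positive if ID50 is at least 10 and either (a) the Visit 1 ID50 is below 10, or (b) where Visit 1 is at least 10, ID50 shows a pre-specified fold rise over Visit 1, for example 3-fold. The fold rise should apply only in case (b). If it were required of everyone, using SAP 7.2's half-limit substitution, the cut-off for participants undetectable at baseline would become 3 × 5 = 15, and true conversions to between 10 and 15 would be lost.

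In SAP 8.4, apply the 8% GTL cut-off to baseline-subtracted peak activity, as is done for luciferase, after checking it against the Central Assay Plan.

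For both assays, report Visit 1 positivity by arm and keep the absolute-threshold call as a sensitivity table.

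The cost is SAP wording and some table programming; the Visit 1 assays are already planned. The downside is that a participant with true low-level activity at baseline needs a larger response to count. The documents do not say whether these results have been seen, so the amendment should record that.
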